Treatment adherence in type 1 diabetes (T1D) tends to decline among adolescents, increasing risks of acute and chronic complications, excess health care use, poorer quality of life, and T1D-related family conflict. Poor adherence is associated with psychiatric and family dysfunction and often persists into early adulthood. Therapeutic advances such as continuous subcutaneous insulin infusion (CSII or "insulin pump") and continuous glucose monitoring (CGM) could improve metabolic control and quality of life. But, teens often do not benefit fully from such advances. Many studies of adults show that patient-centered communication styles predict more favorable clinical outcomes. Shared medical decision making (SMDM) interventions have improved outcomes among adults with diabetes and other conditions. Research in pediatrics has also shown that patient-centered and family-centered communication styles predict favorable outcomes, but most of this research is in primary care and has not studied youth with chronic conditions. Since there have been no controlled trials of SMDM with chronically ill youths, we propose a randomized controlled trial of an SMDM intervention compared with Usual Clinical Practice (UCP). Qualitative interviews of youths and parents who have previously faced these decisions and reliance on expert consultants, pediatric endocrinologists and diabetes educators have preceded this trial and provided valued input for refining the planned intervention and adapting the structured SMDM format for pediatrics. Now, we will recruit and randomize 166 11-<17 year old youth with T1D who are candidates for CSII or CGM (and a parent/caregiver) at all Nemours sites. The SMDM intervention will be delivered via a web-based platform, facilitated by Diabetes Educators (DEs) at each site in a standardized, yet individually tailored format. SMDM will employ multimedia "decision aids" prepared with the award-winning Nemours Center for Children's Health Media and the "e-city interactive" web design firm in Philadelphia in accord with pertinent international standards. SMDM will also include individualized assistance from the DE in assuring that each youth's and parent's preferences, values and cultural beliefs are carefully addressed and communicated to the attending endocrinologist. After a baseline evaluation and randomization to SMDM or UCP, effects on the primary outcome (treatment adherence; device utilization) and secondary outcomes (glycemic control, treatment alliance, decision conflict and regret, treatment satisfaction, diabetes-related distress and self-efficacy) will be measured over 1 year. Mixed effects modeling will be the primary analytic technique for evaluating effects on primary/secondary outcomes, examining selected variables as moderators and mediators of treatment effects, and assessing whether such effects are comparable for the two medical decisions of interest. The results will verify whether SMDM in this context enhances treatment adherence, device use and parent/patient-reported outcomes in youth with T1D.

Support was awarded for Senior Research Coordinator [name], M.A.C.P. as Project Coordinator for 6 calendar months (50% FTE) in all 3 project years. She will have overall responsibility for ensuring the appropriate collection, transmission and management of study data from the clinical sites to Nemours Children's Clinic in Jacksonville. She has performed similar roles in several of [name] prior NIH grants over the past 19 years.

Support was awarded for a 50% Diabetes Educator (DE). This budgeted amount will be dedicated to supporting DEs at each site based on an estimated "extra" time commitment of 6 hours per patient and parent who are assigned to the SMDM group. The DE will see each SMDM family for two study visits: the first visit will be an orientation of the participants to the decision aids and web platform and registration of the family on the website; the second visit will consist of a consultation about the family's experience with the decision aid and the preparation of a post-SMDM assessment report. The DE will transmit the participants' electronic self-assessment generated by the decision aid and the post-SMDM assessment report to the attending endocrinologist for further consideration and discussion with the adolescent and parent.

Support was awarded for 5% FTE appointment for all 3 years of the project for [name]. who will function as the project statistician. [name] has foundation-wide responsibility to provide statistical expertise to investigators at all Nemours sites. He is the statistician on [name] study "Clinician-Patient-Parent Communication in Pediatrics" and they are collaborating on a grant in preparation regarding prevention of child obesity. [name] an expert at such analytic techniques as individual growth modeling, mixed models, and hierarchical growth modeling which are central to the analysis plan for the proposed work.

Support was also awarded for 5%FTE appointments for four pediatric endocrinologists, who will function as co-investigators for all 3 years of this project. These are Drs. [name] (Wilmington, DE), [name] (Philadelphia, PA), [name] (Orlando, FL), and [name] (Pensacola, FL). These physicians have participated in the preparation of this application and will perform several important roles. They participated in the Qualitative Interview Study and helped in engaging other health care providers to do the same, ensuring that the perspectives of expert clinicians and diabetes educators are reflected in the multimedia decision aids and the SMDM intervention. For the randomized controlled trial, they will identify and recruit eligible participants, manage the study patients clinically, coordinate the medical management of enrolled participants and participate in preparing abstracts, posters and journal articles. These physicians have fulfilled similar roles in [name] ongoing NIH-funded trial of continuous glucose monitoring in adolescents with T1DM.

Funds were awarded to support a Research Coordinator/Specialist at each Nemours site throughout the project. The coordinators will probably be recruited from among research coordinators and/or specialists who are already employed at the various sites and they will each be reassigned to this study for at 40% FTE in Year 2 and 50% FTE in Year 3. All of these individuals possess degrees in relevant disciplines and several years of relevant research experience. They will recruit participants and obtain signatures on parental permission and adolescent assent forms. The Research Coordinators will manage the collection of project data and its transmission to the coordinating center. Clinic staff (MD and DE) will identify potentially eligible participants, but all of the other recruitment, informed consent, data collection and other research duties will be the responsibilities of these research staff.

Consultant Costs:

Funds were awarded to support three consultants at \$1,000 per year each for all three years of the project. [name]. of Cincinnati Children's Medical Center has published extensively on shared medical decision making in the context of pediatricians' management of children with attention deficit hyperactivity disorder. [name]. of the Children's Hospital of Philadelphia has also published extensively on this same topic and he is also an accomplished qualitative researcher. [name]. is a board certified pediatric endocrinologist with extensive clinical and research experience in type 1 diabetes. She also directs a Shared Medical Decision Making Service at the Children's Hospital of Eastern Ontario. All three of these physicians has extensive familiarity with the International Patient Decision Aids Standards and they will assist the research team in ensuring that the CSII and CGM decisions developed for this study meet those standards. They are also experts in measurement methods that pertain to shared medical decision making.

Supplies:

Results HbA_{1c} tests conducted routinely at the point of care at each clinic visit for study participants will be retrieved from the EMR for use as a secondary outcome measure. Thus, there will be no laboratory costs incurred to this grant for collection of those important data.

Gathering information about the use of the CGM and insulin pump provides some of the key data for the study. We have budgeted a \$5 payment to adolescents for completing the Insulin Pump Use Profile and \$5 for completing the CGM Use Profile. Noting that some patients will be using two of these types of devices, these amounts total an estimated \$6,640 for the entire study, which has been distributed across project years in the budget. Additional incentives are provided in the form of \$25 gift cards provided to each family in exchange for completing the scheduled questionnaires and other study measures at Visits 1, 3, and 5 during the study, which are the most burdensome of the study visits. These costs total \$12,450 (\$25 X 166 patients X 3 visits/patient) and have been distributed equally across Years 2-3.

KidsHealth/Nemours Diabetes Decision Aids/Multimedia Project

A key category of expenses that will be incurred during the study consists of the costs associated with planning, creating and refining the multimedia decision aids for internet delivery that will be central elements of the proposed SMDM intervention. These costs were estimated in consultation with Nemours Center for Children's Health Media based on their extensive experience in budgeting recent similar projects and include the costs of developing and producing multimedia content for distribution via a web platform. Decision aids will be created for Continuous Subcutaneous Insulin Infusion (insulin pump) therapy and Continuous Glucose Monitoring. A detailed outline of the planned content for each of the decision aids appears in the Appendix. The total of \$342,340 (Year 1: \$247,193; Year 2: \$95,147) reflect the costs estimated based on past production of similar internet educational programs. In Year 1, the requested support would be dedicated to Editorial Costs (Producer, Medical Review, Editing, Scriptwriting, Copy Editing): \$14,832; Design (Art Direction, Illustration, Medical Review): \$22,247; and Production/Post-Production Costs (Producer, Medical Review, Studio rental, Talent fees, Production/shoot days, Music, Audio mixing, Post-production, Web Formatting): \$210,114. In Year 2, the requested support would be dedicated to Editorial Costs: \$5,709; Design: \$8,563; and Production/Post-Production Costs: \$80,875.

KidsHealth's Responsibilities

1. Review and editing of content outlines (to determine what can and can't be incorporated into the video programs)
2. Scriptwriting
3. Pre-production (casting for host, assistance in screening and casting teens and families, shooting locations acquisition)
4. Art Creation (storyboarding and production of medical illustrations and animations upon final approval of scripts)
5. Production (hiring of crew, shooting within Nemours and at off-site locations in DE area)
6. Post-Production (video editing, facilitating review of videos, voiceover recording, music selection)
7. Delivery of a beta-test version of each decision aid for final review and editing by adolescents, parents and health care professionals.
8. Final delivery of Web application

[name] Responsibilities

1. All content research, to be delivered to NCCHM in the form of detailed outlines
2. Assembly of core content review committee, who will review scripts and videos per schedule
3. Review and editing of scripts, medical illustrations/animations, and videos (in various stages of completion) per schedule
4. Search and screening of local teens and families to appear on camera in both speaking and nonspeaking roles

5. Recruitment of Nemours medical staff to appear on camera and as on-set advisors for all clinical scenes
6. Assistance in clearing and acquiring shooting locations within Nemours as needed (e.g. hospital rooms, exam rooms, etc.)
7. Acquisition of all needed props (e.g. various types of insulin pumps, etc.)

About KidsHealth

KidsHealth.org has separate areas for parents, kids, and teens, each with its own focus and flavor – and has a huge, constantly updated library of physician-reviewed, jargon-free content consisting of over 10,000 articles, movies, animations, and other features. In addition, the Center develops a companion site, KidsHealth in the Classroom, which provides free grade-appropriate health curricula to teachers, school nurses, coaches, and others that work with children and teens.

KidsHealth.org has received numerous juried-awards, including 4 Webbys as Best Family/Parenting Site and Best Health Site online. The National Library of Medicine, through its publically-facing Medline Plus site, links to over 1,200 KidsHealth articles. The approach of KidsHealth, which focuses on both “hard” medical issues with emotional issues, is recognized as a model of effective, engaging communication.

In addition to the KidsHealth.org website, the Center provides widely distributed education through partnerships with over 50 of the nation’s children’s hospitals, and well as about 200 other media, governmental, and corporate partnerships - providing them with KidsHealth content as their online education. The Center is the largest single provider of online educational content to children's hospitals in the nation.

Travel:

Support for travel is requested in Year 1 for 4 co-investigators to come to Jacksonville for a study planning meeting. The cost is estimated at \$2,000 per person per trip. Support for travel is requested in Year 1 for 1 investigator to attend a relevant professional conference and in Year 3 for 4 investigators to attend relevant professional conferences. The cost is estimated at \$2,000 per person per trip.

Inpatient Care Costs:

None

Outpatient Care Costs:

None

Consortium/Contractual Costs:

We have established a subcontract with Thomas Jefferson University to cover the personnel costs associated with supporting [name]. for 0.6 calendar months per year (5% FTE) for all 3 years of the project as a Co-Investigator. [name] is a board certified pediatric endocrinologist who will serve as the co-investigator for the Nemours-Jefferson Pediatrics site in a role equivalent to that of Drs. [name], [name] and [name], each of whom are Nemours employees. The TJU fringe benefit rate of 29.3% of salary, and the PCORI indirect cost rate of 40% have been applied to this subcontract. A letter of commitment from Thomas Jefferson University to enter into this subcontract accompanies this application. Note: This subcontract will be voided effective January 1, 2015 when [name] and the other research staff at Nemours-Jefferson Pediatrics will become Nemours employees.

We have established a subcontract with The Barbara Davis Center for Childhood Diabetes, the only freestanding pediatric diabetes treatment center in the US. Affiliated with the University of Colorado College of Medicine and Children’s Hospital of Colorado, BDC manages over 3,300 pediatric patients with type 1 diabetes. A subcontract with the Barbara Davis Center would commit BDC to the recruitment of 80 eligible patients/parents between June 1 and November 30, 2015 and to maintain study follow-up over the following 12 months for each participant. The subcontract would cover the personnel costs (salary plus fringe benefits) for the involvement of [name]. as a co-investigator on this project, [name] CDE as Diabetes Nurse and [name] as Research Assistant.

Other Expenses:

Support was awarded for \$3,000 for publication costs in Year 3 for such expenses as journal page

charges, preparation and printing of posters, graphic and medical illustration services, abstract and poster submission fees and other expenses related to the dissemination of study results.

Support was awarded for reimbursement of 10 members of the Family Advisory Council in the amount of \$500 per year per member to offset their costs for travel, child care, etc. incurred due to their service on this important committee.

We were awarded \$5,000 per year in Years 1 and 2 and \$8,000 in Year 3 to cover the costs of participation incentives in the form of \$25 gift cards per family for questionnaire completion and \$5 gift cards for bringing insulin pumps or CGMs to study visits for downloads. These funds will enable us to offer reimbursement for travel costs, meals, parking and child care for low-income participants, particularly those who are members of racial and ethnic minority groups. Reduction of these practical barriers to study enrollment and retention is critical to achieve the sampling objective of enrolling 24% of the full sample of participants from racial and ethnic minority groups. In addition to its humanistic value, the achievement of sufficient minority representation is crucial from a scientific standpoint since this would permit analyses to determine if the tested intervention is equally effective with important sub-groups of the population.

Equipment:

None

Other Sources of Funding:

None

BIOGRAPHICAL SKETCH

Provide the following information for the key personnel and other significant contributors in the order listed on Form Page 2. Follow this format for each person. **DO NOT EXCEED FOUR PAGES.**

NAME [name]., A.B.P.P.	POSITION TITLE Principal Research Scientist and Co-Director, Center for Health Care Delivery Science; Chairperson, Nemours IRB #2 and IRB #3
eRA COMMONS USER NAME [name]	

EDUCATION/TRAINING *(Begin with baccalaureate or other initial professional education, such as*

INSTITUTION AND LOCATION	DEGREE (if applicable)	YEAR(s)	FIELD OF STUDY
U. of Texas	BS	1972	Psychology
U. of Texas	MA	1976	Psychology
Western Michigan University	PhD	1980	Psychology
Johns Hopkins School of Medicine	Post-Doc	1981	Pediatric Psychology

A. Personal Statement

My role in this project is as Principal Investigator with overall responsibility for study coordination, management of human and fiscal resources and the responsible conduct of the proposed research. I will coordinate the design and production of the two decision aids for internet delivery with our study consultants and our partners at KidsHealth and E-City Interactive. I will oversee both the qualitative interview study in the first year of the project and the randomized controlled trial of shared medical decision making in the latter two years. I will consult with the project statistician about the analysis, interpretation and dissemination of the resultant research findings.

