Part B: Approach-Research Design and Methods: Having completed Specific Aims 1 and 2 in the first 18 months of this grant, we now turn to implementation of a randomized controlled trial of SMDM to evaluate Specific Aim 3.

B.1. Participants:

The planned RCT sample will consist of 166 eligible patients who receive care for type 1 diabetes at any Nemours foundation entity or at the Barbara Davis Center for Childhood Diabetes in Denver, as well as a parent or other legal caregiver of each youth. Enrollment criteria for these patients include: Age, at least 11 but not yet 18 years old, T1D for ≥ 1 year or for at least 6 months and with the most recent Hemoglobin A1c of 7.5% or higher, and facing a decision about CSII or CGM. Access to technological advances in diabetes care may be limited for racial/ethnic minorities, so we will over-sample them to enroll at least 40 youth who are self-identified racial/ethnic minorities (24% of sample). See the Section on Representation of Women and Minorities for how this will be achieved. The enrollment objectives include a minimum of 30 patients facing each treatment decision to facilitate comparisons between them.

Since preparation of the Decision Aid websites has required more time than we expected, and since the funding agency (PCORI) does not now approve no-cost extensions of their funded studies, the work must end by March 31, 2016. Therefore, the duration of follow-up for each enrolled participant will depend on the date of that participant's enrollment as follows: Enrollment before 3/31/15: 12 months; Enrollment 4/1/15 through 6/30/15: 6 months. Enrollment will end on 6/30/15 and data collection will end on 12/31/15, allowing 3 months for data cleaning and verification and completion of statistical analyses. PCORI is considering allowing no-cost extensions and if that happens, the duration of follow-up for late-enrolling participants will be extended.

Enrollment criteria are:

Inclusion Criteria for Youths: Age 11 to not yet 18 years; Physician-diagnosed T1D for at least 1 year or for at least 6 months and with the most recent Hemoglobin A_{1c} of 7.5% or higher (the minimum HbA_{1c} criterion ensures that no patients will enroll in the study who have substantial remaining endogenous insulin secretion. This will preserve the opportunity to evaluate treatment effects on HbA_{1c}, which is an important secondary outcome of the study); Considered by treating HCP to be an appropriate candidate for CSII or CGM

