Demographic and baseline characteristics (age, race, ethnicity, family composition, marital status, SES), primary and secondary end points, and biochemical, psychological, and behavioral variables will be summarized by intervention groups. One way analysis of variance (ANOVA) of each continuous baseline characteristic and a Fisher exact test/chi-square test/CMH test for each categorical variable will be used to compare the intervention groups at baseline. These comparisons will be used to evaluate the balance of demographic and baseline characteristics among intervention groups. Analyses of primary and secondary end points will be adjusted for significantly imbalanced baseline characteristics. For those measures completed separately by parents and youths, when parent and youth scores are correlated at $r > .70$, a combined parent-adolescent score for that variable will enter analyses. Otherwise, separate analyses will be completed on parent and adolescent scores. A mixed models (or multilevel modeling) approach will be used to test the hypotheses listed below.¹⁶⁹⁻¹⁷² The methods advocated by Holmbeck¹⁷³ will be used to evaluate baseline variables that moderate/predict SMDM-UCP treatment effects on primary study outcomes. Candidate moderator variables will include SES, youth age and gender, race/ethnicity, family structure, and health literacy and numeracy. The methods advocated by Holmbeck¹⁷³ will also be used to evaluate variables that may mediate SMDM-UCP treatment effects on primary study outcomes. In each case, these will include measures that are obtained serially and concurrently with the primary study endpoints. SAS subroutines for addressing the potential confounding influences of time- dependent covariates (e.g. youth age) will be employed as needed in these mediational analyses. With five measurement points for HbA_{1c} and hypoglycemia, the proposed mixed models approach will be capable of detecting longitudinal associations among study variables that are non-linear in form.

Hypothesis 1: Compared to UCP, the SMDM group will have significantly more favorable status in terms of indices of optimal use of CSII or CGM, scores on the CSII or CGM Knowledge Test, SURE Test, Decision Regret Scale, Diabetes Technology Questionnaire and SMDM Satisfaction Scale at each follow-up measurement point.

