Hypothesis 2: Compared to UCP, the SMDM group will have significantly more favorable status in terms of scores for treatment adherence (DSMP-SR), HbA_{1c}, and frequency of moderately severe or severe hypoglycemia at each follow-up measurement point.

Hypothesis 3: Effects of SMDM on indices of optimal use of, and satisfaction with, CSII or CGM will be mediated by changes in the measures of decision quality (Test of CSII or CGM Knowledge, Decision RegretScale, SURE Test, Decision Satisfaction Scale).

Hypothesis 4: Significant moderators of benefit from SMDM along the measured outcomes will include baseline measures of socioeconomic status, health literacy and numeracy, youth age, and family structure.

Hypothesis 5: SMDM will have indistinguishable beneficial effects on the primary study outcomes regardless of which clinical decision (CSII or CGM) was the focus of the SMDM intervention.

Statistical Power Statistical power to detect treatment effects of interest on the primary endpoints was assessed using the online DSS Research Statistical Power Calculator.¹⁷⁴ With enrollment of 166 eligible youth and parents and attrition of 10% over the 12-month study, and a resulting “Completer” sample size of 150, the study will have statistical power of .87 to detect a moderate treatment effect of ~0.4 SD on the measures of decision quality and CSII or CGM optimal use. Even though statistical power remains adequate for detection of somewhat smaller treatment effects, effects of less magnitude are unlikely to have sufficient clinical significance to warrant the added cost and inconvenience of implementing SMDM.

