
Part C: INCLUSION OF WOMEN, MINORITIES AND CHILDREN AND HUMAN SUBJECTS PROTECTION

C.1. Representation of Women and Minorities Both studies will enroll a roughly equal proportion of male and female youth with T1D. A substantial majority of participating parents are expected to be women. For the RCT, we will over-sample racial and ethnic minorities so that the enrolled 166 participants include at least 40 youth (24%) who are members of racial or ethnic minorities. In an effort to facilitate enrollment of minorities, we plan to make especially concerted efforts to identify all eligible minority participants through a search of the electronic medical record system, we will contact these families in person wherever we can, we will ask the treating endocrinologists to play a more active role in their recruitment, and we have budgeted funds to enable the study to pay for verifiable transportation and child care costs associated with study participation by low-SES families. In our four most recent studies of the T1D population at Nemours, enrollment of racial and ethnic minorities has averaged 28%, with most of these self-identified as either African American (77%) or Hispanic (20%). In all of the numerous T1D studies conducted by [name] over the past 20 years, the lowest representation of minorities in his studies has been 18%. We also expect to be able to achieve laudable representation of racial and ethnic minorities in the proposed research and we have set a target of 40 such participants (24% of the sample) as the minimum acceptable proportion.

C.2. Inclusion of Children: The RCT will enroll 166 11-<17 year old youth with type 1 diabetes as the primary research participants. At least one parent or other legal caregiver of each youth will also participate.

C.3. Human Subjects Protection

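### Enrolling 40 minority youths cannot show whether SMDM is equally effective across racial/ethnic groups: the 95% CI for the difference in effects would be about ±0.75 SD

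*Combined protocol and SAP*

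**What the plan says.** The budget justification (Other Expenses) ties reimbursement of low-income families to the 24% minority enrollment objective. It calls adequate representation scientifically essential because "this would permit analyses to determine if the tested intervention is equally effective with important sub-groups of the population". Section C.1 fixes the number: "we have set a target of 40 such participants (24% of the sample) as the minimum acceptable proportion". B.1 and C.3 repeat the figure of at least 40 of 166.

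In B.5, the analysis that would carry this out is the moderator analysis: "Candidate moderator variables will include SES, youth age and gender, race/ethnicity, family structure, and health literacy and numeracy". B.5 also provides for exploratory subgroup analyses where needed. It sets all tests as two-sided at 0.05 and allows results to be given as a 95% confidence interval, a p-value or both. The Statistical Power paragraph covers only the overall SMDM versus UCP comparison: power 0.87 for about 0.4 SD with 150 completers. It gives no power for any interaction or subgroup, and no margin that would define equal effectiveness.

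**The concern.** Determining whether an intervention is equally effective in two groups requires a reasonably precise estimate of the difference between the two treatment effects. With about a quarter of 166 participants in one group, that estimate is much less precise than the overall effect, and the documents never say how precise it would be. The stated reason for the enrollment objective is therefore a property that the design has not been shown to have.

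What is at stake is how a null interaction would be understood. If the test would usually miss a complete absence of benefit in minority youths, a non-significant result says almost nothing about equality. Because B.5 allows a p-value alone, the imprecision could go unseen by a reader who has been told that the sample permits this determination.

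**Working it through.** **Inputs from the documents**
- Minority youths: at least 40 of 166, so 126 others (B.1, C.1).
- Attrition 10%, giving about 150 completers; target effect about 0.4 SD, with smaller effects described as unlikely to justify the intervention (B.5, Statistical Power).
- Equal allocation (Randomization Procedures), stratified by site only (B2).
- Two-sided 0.05 (B.5).

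**Assumptions not in the documents**
- SD = 1 in both groups.
- Attrition equal in both groups: 40 × 0.9 = 36 and 150 − 36 = 114.
- Even split between arms within each group.
- Benchmark interaction of 0.4 SD: the full target effect in one group and none in the other.

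**The plan's own figure.** It states overall power only. With 75 per arm, SE = √(2/75) = 0.163 and power = Φ(0.4/0.163 − 1.96) = 0.69, not 0.87. That discrepancy is a separate matter. It is carried below only as a sensitivity case.

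**Interaction, completers**
- The treatment effect in a group of n split 1:1 has variance 4/n.
- SE = √(4/36 + 4/114) = √0.1462 = 0.382 SD.
- 95% CI half-width = 1.96 × 0.382 = 0.75 SD.
- Detectable with 80% power = (1.96 + 0.84) × 0.382 = 1.07 SD.
- Power at 0.4 SD = Φ(0.4/0.382 − 1.96) = Φ(−0.91) = 0.18.

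**Interaction, all enrolled (40 vs 126)**
- SE = √(4/40 + 4/126) = 0.363 SD; half-width 0.71 SD; detectable 1.02 SD; power at 0.4 SD = 0.20.

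**Effect within the minority group alone**
- 18 per arm: SE = √(2/18) = 0.333; power at 0.4 SD = Φ(1.20 − 1.96) = 0.22. With 20 per arm it is 0.24.

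**Sensitivity of interaction power**

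| Case | Power |
|---|---|
| 36 vs 114, interaction 0.2 SD | 0.08 |
| 36 vs 114, interaction 0.4 SD | 0.18 |
| 36 vs 114, interaction 0.8 SD | 0.55 |
| 36 vs 114, interaction 1.0 SD | 0.74 |
| 46 vs 120 (28% minority), 0.4 SD | 0.21 |
| SD 0.794, the value at which 0.87 overall power would hold, 0.4 SD | 0.26 (completers), 0.28 (enrolled) |
| 40 vs 126, variance halved, 0.4 SD | 0.34 |

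In the last row, SE = 0.363 × √0.5 = 0.257, so the 95% CI half-width is 1.96 × 0.257 = 0.50 SD. Even there, an interval centred on zero would include a difference as large as the whole 0.4 SD target effect.

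**Scale of the shortfall.** For 80% power at 0.4 SD with a 24% minority share, total N = (2.80/0.4)² × 4 × (1/0.241 + 1/0.759) ≈ 1,073.

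**The case against.** The strongest reply is that the sentence belongs to a budget justification, not the analysis plan. It states no test, margin or decision rule. B.5 already treats subgroup analyses as exploratory and names race/ethnicity only as a candidate moderator, and no hypothesis claims equal effect by race/ethnicity. B.5 also provides for confidence intervals. All of this stands, and it makes the point minor. It does not remove it. The sentence is the stated scientific reason for a recruitment objective, the moderator analysis takes it into B.5, and B.5 does not require the interval.

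A second reply is that mixed models and a Full Analysis Set needing only one post-baseline record give more information than a single comparison of completers. That is fair, and it is why a range is shown. The top of the range, 34%, is still low.

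Three stronger readings are tempting, and the documents do not support them.

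- **That a null interaction will be reported as equality.** Nothing says so. The gap is that nothing rules it out.
- **That over-sampling is contradicted by a 24% target below past enrollment.** C.1 reports that in recent Nemours studies "enrollment of racial and ethnic minorities has averaged 28" percent, but 40 is explicitly a floor. It also exceeds the lowest past figure of 18% and lies at the bottom of the 24%-31% range in C.3. The 28% is a Nemours figure, whereas the sample includes 80 planned recruits from the Denver center and remote recruits, for whom no minority share is given. B.1 adds that minority access to these devices may be limited, so past diabetes studies may not describe the pool of candidates.
- **That B.5 contradicts itself because Hypothesis 4 leaves out race/ethnicity.** Hypothesis 4 predicts which moderators will prove significant: "Significant moderators of benefit from SMDM along the measured outcomes will include baseline measures of socioeconomic status, health literacy and numeracy, youth age". One further item, on family make-up, completes its list. That list can properly be a subset of the candidates.

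**Conclusion.** The point holds as a minor one. The planned sample cannot determine whether SMDM is equally effective in minority and other youths. With 36 and 114 completers, the difference in effects would carry a 95% CI of about ±0.75 SD, nearly twice the target effect, and only interactions near 1.1 SD would be detected with 80% power.

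Power is about 18% at the 0.4 SD benchmark. It ranges from about 18% to 34% across completer or enrolled counts and an assumed variance reduction of 0-50%. These figures rest on unit SD, equal attrition and an even split between arms within each group. Stratification is by site only, so the split is not guaranteed, and any imbalance would widen the interval. The benchmark is a choice of this review, but the interval width does not depend on it.

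No primary endpoint, hypothesis or main comparison is affected. The word over-sample and the differing moderator lists are not part of this finding.

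**What to change.** In the budget justification (Other Expenses), replace the claim that the sample permits a determination of equal effectiveness. Put the same statement beside the moderator analysis in B.5. Suggested text:

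> The race/ethnicity-by-arm interaction is exploratory. It will always be reported as an estimate with its 95% confidence interval, not as a p-value alone. A non-significant interaction will not be reported as evidence of equal effectiveness. With about 36 minority and 114 other completers, the interaction detectable with 80% power is about 1.1 SD.

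This agrees with the exploratory status that B.5 already gives subgroup analyses. It narrows one option there, because the interval becomes mandatory for this analysis. The cost is wording and a less favourable claim. It needs no added participants, data or analyses, and the minority enrollment objective can stay as it is.
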